### 15.9. Suspension or Early Termination

Medtronic reserves the right to suspend or terminate the study at any time. Reasons may include, but are not limited to, the following:

[figure not shown]
- Insufficient enrollment to complete the study within the expected timeframe
- Identification of unacceptable safety profile; suspicion of an unacceptable risk will result in a suspension, confirmation of an unacceptable risk will result in termination
- Product performance/product supply issues
- EC/IRB/the governing regulatory authority (if applicable) suspension and/or termination of the study

Medtronic reserves the right to suspend or terminate the study at an individual site. Reasons may include, but are not limited to, the following:

- Noncompliance with the protocol
- Serious or repeated deviations at the site
- Failure to implement required corrective and preventive actions
- Insufficient enrollment to complete the study within the expected timeframe
- Loss of appropriately trained site personnel

Investigators are required to notify the IRB/EC of study suspension/termination. Subjects will be notified by the investigator of suspension/termination due to unacceptable risk or of termination due to any other cause.

If, for any reason, Medtronic suspends or prematurely terminates the investigation at an individual investigation site, Medtronic shall inform the responsible regulatory authority as appropriate and ensure

[figure not shown]

that the IRB/EC is notified, either by the Principal Investigator or by Medtronic. If the suspension or premature termination was in the interest of safety, Medtronic shall inform all other Principal Investigators and investigational sites. The Principal Investigator or authorized designee shall promptly inform the enrolled subjects at his/her investigation site, if appropriate.

[figure not shown]

### 17. Appendices

Not applicable

[figure not shown]
### 18. Version History

[figure not shown]
#MDT16075 Version 4.0

Page 78 of 81

[figure not shown]
Medtronic

# OPuS One Clinical Investigation Plan #MDT16075 Version 4.0 Page 79 of 81 Medtronic

## OPuS One Clinical Investigation Plan #MDT16075 Version 4.0 Page 80 of 81 Medtronic

[figure not shown]

### 1. Version History

Version	Summary of Changes	Author(s)/Title

### 2. List of Abbreviations and Definitions of Terms

Abbreviation	Definition
AE	Adverse Event
BPI	Brief Pain Inventory
CIP	Clinical Investigation Plan ('Protocol')
DD	Device Deficiency
MedDRA	Medical Dictionary for Regulatory Affairs
PT	Preferred Term
RF	Radiofrequency
SAE	Serious Adverse Event
SAP	Statistical Analysis Plan
SOC	System Organ Class

### 3. Introduction

The OsteoCool™ RF Ablation system is indicated in the United States (US), Europe (EUR) and Canada (CAN) for patients with metastatic malignant lesions in a vertebral body, painful metastatic lesions involving bone (in the US, patients with metastatic lesions involving the bone must have failed or were not candidates for standard therapy) and benign bone tumors such as osteoid osteomas.

The purpose of this prospective, multi-center, non-randomized, single arm study is to evaluate the effectiveness of the Medtronic OsteoCool™ RF Ablation system.

The scope of this Statistical Analysis Plan (SAP) includes the Primary Objective Report and the Final Study Report. The primary objective hypothesis will be tested and reported after the sample size requirements for it have been met, and a final study report will be prepared after final study data is collected.

### 4. Study Objectives

### 4.1 Primary Objective(s)

To demonstrate an improvement from baseline to 3 months post radiofrequency ablation in worst pain score in the past 24 hours in subjects treated for metastatic lesions in only the thoracic and/or lumbar vertebral body(ies).

Worst pain score at the target treatment site will be collected from the Brief Pain Inventory (BPI).

Revision 1.0

Page 4 of 15

### 4.2 Secondary Objective(s)

To characterize change from baseline to 3 months post radiofrequency ablation in worst pain score in the past 24 hours in subjects treated for metastatic lesions in the periacetabulum, iliac crest, and/or sacrum, and for benign bone tumors.

Worst pain score at the target treatment site will be collected from the BPI.

### 4.3 Additional Measures

### 4.4 Safety Measure

To characterize incidence of all device, procedure and/or therapy related adverse events and device deficiencies from enrollment to the 12-Month Visit.

### 5. Investigation Plan

This is a prospective, multi-center, non-randomized, post-market, single arm study designed to provide effectiveness outcomes on the Medtronic OsteoCool™ RF Ablation system.

The start of the study for each subject is defined as the date the subject first signs the informed consent. Enrolled subjects who do not meet baseline eligibility or who do not undergo the OsteoCool procedure will be exited from the study (e.g. RF therapy was not delivered). The completion of the study for each subject is defined as the conclusion of the 12 Month Visit (Study Exit). Each subject's participation in the study is expected to last approximately 1 year from the date of the OsteoCool procedure. Each subject will be evaluated prior to the OsteoCool procedure, during the procedure, prior to hospital discharge, 3 days, 1 week, 1-, 3-, 6-, and 12-months post procedure.

There is no randomization in the study.

Revision 1.0

Page 5 of 15

After the sample size requirements for the primary objective hypothesis have been met, there will be a snapshot, and a *Primary Objective Report* will be prepared. The report will include testing of the primary objective hypothesis and only brief summaries of study subjects, non-primary objective efficacy and safety. The study will continue enrolling and following subjects after the report.

At the conclusion of the study, the data will be locked, and a *Final Study Report* will be prepared, which will include all evaluations (other than the primary objective). Additional subjects enrolled and treated for metastatic lesions involving only the vertebral body, that were not included in the Primary Objective Report will be combined with the subjects in the Primary Objective Report and summarized together in the Final Study Report. The primary objective will not be re-tested in this report. However, the results of the original primary objective hypothesis testing will be included for completeness.

Figure 5-1 outlines the study design and required follow-up requirements.

Revision 1.0

Page 6 of 15

[figure not shown]

Figure 5-1: Study Design

[figure not shown]
### **Enrollment** Obtain informed Consent Baseline Verify eligibility criteria, obtain pregnancy test collect demographic, cancer history, baseline images at the target site(s) if available, Karnofsy Performance Scale (not for benign bone tumors), concomitant medications/treatments, BPI, EQ-5D-5L, EORTC-QLQ-C15-PAL (not for benign bone tumors), reportable adverse events/device deficiencies and deviations ≤21 days after baseline visit Enrollment, Baseline and RF ablation can occur on the same day OsteoCool Procedure Day 0 Collect RF ablation procedure and OsteoCool details, reportable adverse events/device deficiencies, deviations, concomitant medications/treatments, and Generator data uploads Study Was the RF therapy Discontinuation delivered? Yes **Prior to Discharge** Collect worst pain only, PI's self-assessment on local tumor control, post-treatment images (if available), deviations, and reportable adverse events/device deficiencies 3 days ± 2 Days after Day 0 1 week (7 days) ± 2 Days after Day 0 1-Month Visit 30 days ±15 Days after Day 0 3-Month Visit 90 Days ± 30 Days after Day 0 6-Month Visit 180 days ± 59 Days after Day 0 12- Month Visit 365 days ± 90 Days after Day 0

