#### **Table 9-1: Schedule of Events**

Events	Enrollment Baseline 	OsteoCool Procedure (Day 0) 	Prior to Discharge or within 12 hours of the procedure	3 days, 1 week, 1- ,3-,6-, and 12- Month Visits & unscheduled visits 	Phone eCRF (if needed)
Informed Consent Form 	Х				
Eligibility (Inclusion/Exclusion Criteria)	Х				
Pregnancy Test (Women of child-bearing potential)	X				
Demographics and Disease Characteristics	Х				
Karnofsky Performance Scale 	X 				
OsteoCool / procedure details		Х			
	Х	Х	х	Х	Х
Generator data uploads (if available)		Х			
PI assessment of local tumor control (optional)		х		х	
Concomitant cancer and/or tumor treatments, relevant to the target site(s)	х	Х		Х	Х
Concomitant pain medications 	Х	Х		Х	Х
Worst pain score only			Х		
BPI (Short Form) – includes worst pain score in the past 24 hours	Х			х	Х
EQ-5D-5L	х			Х	Х
EORTC-QLQ-C15-PAL 	X 			X 	
Deviations	Х	Х	X	X	Х
Event Review (AE/DD)	Х	Х	Х	X	Х

- 1) Informed consent must be obtained prior to performing any study-specific procedures.
- 2) Baseline Visit, Enrollment Visit and procedure can occur on the same day. Baseline visit shall be performed ≤ 21 days before the OsteoCool procedure
- 3) Oral narcotics within past 24 hours
- 4) Not applicable for subjects with benign bone tumors
- 5) Unscheduled visits will only be collected for visits conducted in the context of the study

Page 35 of 81

Table 9-2: Protocol Visit Windows\*

Visit	Visit ranges		
Enrollment/Baseline	NA		
Procedure (Day 0)	≤21 days after Baseline visit		
Discharge	Prior to hospital discharge or within 12 hours of the procedure		
Monthly Clinic Visits	3 Days: 3 days ± 2 Days after Day 0 1 week: 7 days± 2 Days after Day 0 1-Month Visit: 30 days ± 15 Days after Day 0 3-Month Visit: 90 days ±30 days after Day 0 6 Month Visit: 180 days ±59 days after Day 0 12 Month Visit: 365 days ± 90 days after Day 0		

\*Every attempt should be made to complete the required onsite clinic visit. However, if a subject is unable to complete an onsite follow-up visit due to physical circumstances, a Phone follow-up visit eCRF can be completed by the Investigator/RC to obtain the required data elements.

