### **6.** Determination of Sample Size

#### **Primary Objective Sample Size**

The sample size calculations were performed using PASS 11 statistical software. (PASS 11 v. 11.0.7, Hintze J).

The primary objective is to demonstrate an improvement from baseline to 3 months post radiofrequency ablation in worst pain score in the past 24 hours in subjects treated for metastatic lesions involving only the vertebral body.

The standard deviation of change from Greenwood et al (2015) is estimated to be 4.1 at 4 weeks. The standard deviation of change in the CAFE study Berenson et al (2011) was 3.2 at 1 month. The standard deviation of change from Lane et al (2011) is estimated to be 2.4 at 1 day post-procedure. It is not known which of those studies will most closely match the population and test conditions in this study. The median of those 3 studies is 3.2. To account for this study having a longer follow-up period and a more diverse patient population, and thus more opportunity for variability, the standard deviation for our sample size calculation will be increased to 3.5.

The minimal clinically important difference (MCID) of 2 points was used to interpret pain score differences in terms of clinical relevance in Bagla et al (2016) and a clinically significant change in pain of 2 points was also identified in Greenwood (2015). This will be used for our calculations.

Bagla (2016) followed subjects for 3 months post procedure. They reported that pain scores were provided for 68% of subjects (32% not provided) at 3 months. This will be used for our calculations.

The PASS program used to calculate the sample size was the one-sample t-test power analysis, mean0=0, meanA=2, standard deviation (of change) =3.5, two-sided significance level (alpha)=0.05, and power=0.90. The required sample size was 35. To account for subjects getting treated but not providing the 3-Month data, the treated sample size is adjusted for a 32% loss, to 52.

A sample size of 35 subjects successfully treated and completing the pain assessment at 3 months is expected to provide results that will be considered relevant to clinicians, as well as provide acceptable power to test the primary objective.

Sample size requirements were only calculated for the primary objective. There are no sample size requirements for the secondary objective and the additional objectives.

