### 7.9 Evaluation of Objectives

The primary objective hypothesis will be tested after the sample size requirements for it have been met. The sample size requirement is 35 subjects successfully treated and completing the pain assessment at 3 months. Prior to the date the 35th subject completes the 3-month visit, the visit cut-off date will be estimated for the database snapshot. If additional subjects are enrolled later and also treated for metastatic lesions involving only the vertebral body, those additional subjects will be combined with the first group and summarized together in the Final Study Report. However, no additional hypothesis testing will be performed in the Final Study Report.

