In the Primary Objective Report, the sensitivity analyses will include Treated Analysis Set subjects that have procedure dates before the last subject's procedure date in the Completers Analysis Set. In other words, subjects recently treated, but not expected to have been followed for the whole 3 months at the time of the snapshot, will not be in the sensitivity analyses.

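### The SAP's procedure-date rule does not keep unfinished 3-month visits out of the primary-report sensitivity analyses, and no same-subject check of the single test against the locked data is planned

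*Combined protocol and SAP*

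**What the plan says.** **Timing of the test.** SAP 5 (Investigation Plan) states: "After the sample size requirements for the primary objective hypothesis have been met, there will be a snapshot". The Primary Objective Report follows from that snapshot. The same section mentions a data lock only at the end of the study, and says of the Final Study Report: "The primary objective will not be re-tested in this report". The original test result is carried into that report. Vertebral-only subjects enrolled later are pooled with the tested ones for descriptive summaries and confidence intervals.

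**Cut-off.** SAP 7.9 sets the requirement at 35 completers and adds: "Prior to the date the 35th subject completes the 3-month visit, the visit cut-off date will be estimated for the database snapshot".

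**Who is analysed.** The primary test uses the Completers Analysis Set without imputation (SAP 7.1.3, 7.4, 7.9.1). Multiple imputation and last observation carried forward (LOCF) are sensitivity analyses on the Treated Analysis Set. In the Primary Objective Report these are limited to subjects whose procedure date precedes that of the last subject in the Completers set. SAP 7.9.1 explains the purpose: recently treated subjects "not expected to have been followed for the whole 3 months at the time of the snapshot, will not be in the sensitivity analyses".

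**Visit window.** CIP Table 9-2 gives "3-Month Visit: 90 days ±30 days after Day 0", so a valid visit can fall from day 60 to day 120.

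**The concern.** The rule and its stated purpose do not match. The rule ranks subjects by procedure date. Whether a subject's 3-month follow-up is finished depends on whether that subject's own window has closed. With a window 60 days wide, a completer who attends early can overtake people treated before them. Those people fall inside the sensitivity set with no 3-month score, although nothing is missing yet.

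Three outputs of the Primary Objective Report are affected:

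- the LOCF result, which carries forward an earlier score (typically the 1-month score) for a visit that is only pending;
- the multiple-imputation result, which fills in a value that may soon be observed;
- the counts of missing data, which SAP 7.4 wants reported to judge the potential for bias.

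SAP 7.9.1 assigns these analyses to the Primary Objective Report, and the SAP schedules no repeat for the primary objective once the visits have closed.

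A related gap concerns the test itself. If a tested subject's pain score or visit date is corrected after the snapshot, the p-value in the final report stays as it was. The final summaries do not show the discrepancy, because they mix the tested subjects with later enrollees.

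**Working it through.** **1. The plan's own figures.** SAP 6 gives "standard deviation (of change) =3.5, two-sided significance level (alpha)=0.05, and power=0.90", a mean change of 2 points, and "The required sample size was 35". For a one-sample two-sided t-test at n = 35, the noncentrality is (2/3.5) × √35 = 3.38 and the critical value is t(34) = 2.032. Power is 0.907; at n = 34 it is 0.899, so 35 is reproduced. Allowing for 32% loss, 35/(1 − 0.32) = 51.5, rounded up to 52. Both figures stand.

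**2. The rule against the window.** Let the last completer be treated on day T and seen at follow-up day 60, with the cut-off on that date, T + 60. A subject treated x days earlier has then been followed for 60 + x days. The window is still open while 60 + x < 120, that is, for any x below 60. For x = 1, follow-up is 61 days and 59 days of window remain. This subject satisfies the procedure-date rule, so is included and imputed, but has not been followed for the whole period. The rule therefore fails on its own terms.

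**3. How many subjects.** The documents do not give accrual or visit timing, so these are assumptions:

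- Accrual: 1.5 to 4.5 vertebral-only subjects a month. The plan implies about 100/36 = 2.8, from a goal of 100 (SAP 6) and about 3 years of enrolment (CIP 6.1).
- Completion: 68% (SAP 6).
- Visit day: uniform on 60 to 120, or normal with mean 90 and SD 10 or 12, clipped to the window.
- Cut-off: the day of the 35th completion. The rule is read as on or before the last completer's procedure date.

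Simulated averages (20,000 replicates per setting):

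| Accrual per month | Visit timing | No score, window open | Of these, would later give a score | Size of set |
|---|---|---|---|---|
| 1.5 | normal, SD 10 | 0.70 | 0.21 | 51.7 |
| 1.5 | uniform | 0.94 | 0.40 | 52.0 |
| 2.8 | normal, SD 10 | 1.36 | 0.42 | 52.0 |
| 2.8 | uniform | 1.89 | 0.82 | 52.5 |
| 4.5 | normal, SD 10 | 2.33 | 0.74 | 52.4 |
| 4.5 | uniform | 3.26 | 1.42 | 53.3 |

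SD 12 falls between the two timings at each rate. The open-window column is an upper figure, because some of those subjects will already have died or left the study. With accrual taken from 1.4 to 5 a month and the cut-off moved by up to 30 days either way, the open-window average ranges from about 0.2 to 3.7.

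**4. Effect on the outputs.** About 52 − 35 = 17 subjects in the set have no score. Those who would later give one are roughly 0.21/16.7 = 1% to 1.42/18.3 = 8% of the reported missing. As an illustration, if each pending score differed from its imputed value by 2 points (the plan's clinically important difference), the Treated-set mean would move by at most 1.42 × 2/53.3 = 0.05 points.

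**5. Later corrections to tested subjects.** Changing one score by d points moves a mean of 35 by d/35: 0.06 for 2 points and 0.29 for the extreme case of 10. The confidence-interval half-width at SD 3.5 is 2.032 × 3.5/√35 = 1.20.

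**The case against.** The strongest reply is that little here can change the conclusion. SAP 7.9.1 already tries to deal with pending visits and states its aim, the number left over is small, and SAP 7.4 requires the timing and reasons for missing data to be reported, which may reveal pending visits. This stands as to size. It does not repair the rule: an imputed value is still used for a visit that may yet take place.

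On the snapshot, the bar on re-testing has a good purpose. It prevents a second test after more subjects accrue, and so supports the absence of a multiplicity adjustment in SAP 7.5. Corrections also reach the final descriptive estimate and interval. Both points are right, but that interval is for a larger group and cannot show whether the tested result is reproduced.

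A reader might infer three stronger things that the documents do not support:

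- *That pending visits count as missing in the primary test.* They do not; that test uses completers only, with no imputation.
- *That the snapshot data are uncleaned.* The SAP does not mention a freeze, but silence does not establish this. CIP 15.1 and 15.2 describe source verification, edit checks, discrepancy resolution and an audit trail.
- *That estimating the cut-off in advance allows an underpowered test.* SAP 5 and 7.9 make the test conditional on 35 completers.

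**Conclusion.** The concern holds in a limited form. The procedure-date rule in SAP 7.9.1 does not achieve its stated purpose under a day 60 to 120 window. This follows from the text and needs no assumption. How many subjects it affects does rest on assumed accrual and visit timing: on average about 0.2 to 1.4 who would later supply a score, and 0.7 to 3.3 with an open window, of about 52. The effect is confined to the sensitivity analyses and missing-data counts of the Primary Objective Report. The sample size of 35 completers and 52 treated is unaffected.

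The missing same-subject check is a second, modest gap. Nothing shows that corrections will occur or would reverse the result. But this is the trial's only test, and as planned the final report could carry a p-value that its own locked data do not reproduce, with no analysis that would show it.

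**What to change.** **Sensitivity set: choose one.**

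- *Redefine the set.* Include vertebral-only Treated subjects whose 3-month window has closed by the snapshot cut-off (procedure at least 120 days earlier), or who already have a 3-month score, or who have exited the study. This costs SAP wording only. Its drawback is that recently treated subjects enter only if their outcome is already settled, which favours early attenders and early exits.
- *Move the snapshot.* When the 35th score is in, fix the procedure-date limit at the last completer's date, and take the snapshot once the window has closed for everyone treated up to it. This is cleaner and also brings late attenders into the Completers set. It delays the Primary Objective Report by up to about 60 days (day 120 minus day 60).

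**Reproducibility check.** At final lock, repeat the identical analysis on the identical subjects, label it as a check, and report any difference from the snapshot result. It adds no subjects and makes no new alpha claim. SAP 5 and 7.9 need a sentence separating this check from the barred re-test. The cost is one program re-run.

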### 3 days, 1 week, 1-, 3-, 6- and 12- Month Visits Post Procedure

Collect reportable adverse events/device deficiencies, deviations, concomitant, PI's self-assessment on local tumor control, medications/treatments, BPI, EQ-5D-5L, EORTC QLQ-C15-PAL (not applicable for benign bone tumors), and follow-up images (if available)

Revision 1.0

Page 7 of 15

### **6.** Determination of Sample Size

#### **Primary Objective Sample Size**

The sample size calculations were performed using PASS 11 statistical software. (PASS 11 v. 11.0.7, Hintze J).

The primary objective is to demonstrate an improvement from baseline to 3 months post radiofrequency ablation in worst pain score in the past 24 hours in subjects treated for metastatic lesions involving only the vertebral body.

The standard deviation of change from Greenwood et al (2015) is estimated to be 4.1 at 4 weeks. The standard deviation of change in the CAFE study Berenson et al (2011) was 3.2 at 1 month. The standard deviation of change from Lane et al (2011) is estimated to be 2.4 at 1 day post-procedure. It is not known which of those studies will most closely match the population and test conditions in this study. The median of those 3 studies is 3.2. To account for this study having a longer follow-up period and a more diverse patient population, and thus more opportunity for variability, the standard deviation for our sample size calculation will be increased to 3.5.

The minimal clinically important difference (MCID) of 2 points was used to interpret pain score differences in terms of clinical relevance in Bagla et al (2016) and a clinically significant change in pain of 2 points was also identified in Greenwood (2015). This will be used for our calculations.

Bagla (2016) followed subjects for 3 months post procedure. They reported that pain scores were provided for 68% of subjects (32% not provided) at 3 months. This will be used for our calculations.

The PASS program used to calculate the sample size was the one-sample t-test power analysis, mean0=0, meanA=2, standard deviation (of change) =3.5, two-sided significance level (alpha)=0.05, and power=0.90. The required sample size was 35. To account for subjects getting treated but not providing the 3-Month data, the treated sample size is adjusted for a 32% loss, to 52.

A sample size of 35 subjects successfully treated and completing the pain assessment at 3 months is expected to provide results that will be considered relevant to clinicians, as well as provide acceptable power to test the primary objective.

Sample size requirements were only calculated for the primary objective. There are no sample size requirements for the secondary objective and the additional objectives.

